2.2 Secondary Objectives

To investigate the effect of Linagliptin treatment on serum endothelium inflammatory markers including: C-reactive protein (hs-CRP), IL-6, TNF-alpha, and fasting lipid profile including ApoA1 and ApoB (5, 6, 30, 36).

Glycemic control will be evaluated by measuring fasting blood glucose, insulin levels and HbA1c. Fasting blood glucose, insulin and lipid profile will be used to assess insulin resistance (32, 37)

Adiposity will be measured using the Tanita Body Composition Analyzer scale, measured as percentage body fat (33). Serum will be used to estimate levels of SDF1-Alpha, VEGF, and GLP1 levels by ELISA (25, 28, 29, and 30).

We also intend to follow resting Metabolic Rate at baseline, midway, and post DPP4 inhibitor therapy to ascertain if Linagliptin has any effect on RMR (56).

Kidney health will be monitored by creatinine clearance and microalbumin/ creatinine levels, which will be obtained from the spot urine sample.

- a. *Subjects will have the option of opting into a sub-study that is being where 10-20 mL of the excess fresh spot urine that has been collected will be used for exosome analysis. This is optional, and is not required of subjects. For details of urine-exosome study please see the appendix.*

[figure not shown]
The biochemical or bio-inflammatory markers are an important marker of endothelial inflammation and dysfunction along with glycemic markers and markers of arterial stiffness (36-43, 55, 57). Literature suggests that DPP4 inhibitors and GLP1 modifies and modulates hemopoietic stem cells and vaso dilatation (37, 44, 45).

Vessel health will be assessed by degree of arterial stiffness, using arterial tonometry. The central and the aortic pressure is assessed by pulse wave analysis (PWA) and pulse wave velocity (PWV) . Arterial stiffness will be assessed using vascular flow and wave form analysis equipment, SphygmoCor CP system from ATCOR. (56)

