DPP-4 Inhibitors may have cardio-protective effects of their own, as they increase bio-availability of endogenous GLP-1. They improve blood flow and nitric oxide production in

endothelium (28, 29). These are unique properties not demonstrated by other oral diabetes medications (29). The mechanism underlying these effects may be mediated by increased nitric oxide bioavailability but is not completely known. However these beneficial effects appear to be independent of glycemia reduction.

It is however unknown whether Linagliptin will have any positive effect on human EPC function where two prominent cardiovascular risk factors co-exist such as CKD and type 2 diabetes.

Therefore we plan to investigate if Linagliptin can alter function and gene expression of CD34+ cells in a setting of CKD and type 2 diabetes. We choose to look at non geriatric adult population with early type 2 diabetes (≤ 15 years of duration) at an early phase of renal impairment (stages 1-3).

We specifically choose to exclude known CVD disease patients and early type 2 DM patients with early CKD as this cohort may be still retain capability to reverse or halt persistent endothelial damage seen in type 2 diabetes and CKD (3,30,35).

Our preliminary study results , which just finished, looked at effect of 150min/week of aerobic physical activity on EPCs in pre-diabetes population show that interventions even though non pharmaceutical can lead to quick (within 4 weeks) improvement in gene expression and function of CD34+ cells. These cellular changes are reproducible and consistent with other outcome measures such as serum biochemistry and vessel wall dilation measures such as flow mediated dilatation. (34)

Research Hypothesis:

We hypothesize that Linagliptin, a member of DPP-4 inhibitor group of drugs may be able to improve number and function of CD34+ endothelial progenitor cells by up-regulating chemotactic agent SDF1 alpha (DPP-4 degrades SDF-1) and its receptor CXCR4 (7, 20, 21) and thereby improving EPC migration and overall endothelial function. We also propose that this expected cardiovascular benefit is independent of HbA1C reduction. (30, 31)

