3 INVESTIGATIONAL PLAN

3.1 Study Design and Duration

Study Schema, 40 Type 2 diabetic Subjects Aged 40-70 on stable dose of Insulin, Metformin, or both

+/- 3 day window for visits

*Assessed at week 0, 6 and 12: Biochemical and cellular markers of endothelial function and Pulse wave analysis and velocity (PWA and PWV), REE and Adiposity.

Week 16 - A telephone call to subjects will be made 30 days after last dose of study medication to determine if there have been any adverse events.

Available related studies and Expected Results: Studies measuring changes to EPCs in type 2 diabetes patients are very limited. To the best of our knowledge there are no studies examining the effect of Linagliptin in type 2 diabetes patients with CKD.

Use of CD34 positive cells as a cardiovascular risk surrogate has been reported in the past. Various studies (11, 34), have shown that various disease states, including those seen in diabetes, can deplete and damage EPC, thereby diminishing their regenerative potential. The inability to maintain or repair damaged endothelial tissue leads to cumulative vascular dysfunction and cardiovascular disease.

We hypothesize that monitoring **number, function and gene expression of endothelial progenitors will allow us to quantify cardiovascular disease risk at the onset and regenerative potential post intervention at a cellular level. It will also help us to identify and correlate the best endothelial function bio-chemical inflammatory marker as an early indicator of cardiovascular disease progression in early type 2 diabetes with CKD and identify patients that are responders.**

Linagliptin along with other gliptins can increase SDF1 alpha levels and possibly CXCR4 receptor expression which will help EPC mobilization and gene expression of hemopoietic CD34 positive stem cells.

Linagliptin 5 mg or placebo will be added to patients who have type 2 diabetes diagnosed ≤ 15 years with HbA1C of 6.5 to 10 % (both inclusive) while being on Insulin, metformin, or both.

Insulin will be titrated upwards if HbA1C is above 10% with minimal dose adjustments so as to keep the adjusted HbA1C below overtly uncontrolled levels (above 10%).

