2. CD34
3. CD309 (VEGFR2-KDR)
4. CD184 (CXCR4), receptor substrate for SDF1 alpha
5. CD31 (PECAM-1, a mature circulating endothelial cell marker)
6. CD133 (a progenitor marker)
7. CD144 (Vascular Endothelial cadherin)
8. Sytox Blue OR Propidium Iodide staining (to detect apoptotic cells)
9. Combinations of 2+3+4+8, to assay percentage of double or triple positive cells
10. (3+4+5+8), to assay percentage of double or triple positive cells
11. 500,000 CD34+ cells, post column will be stained with – PE labelled + Sytox Blue (as a quality control measure, post column)

B. Plate 5 million cells in each well of a 6 well or 12 well plates (2 million) BD Biosciences Human Fibronectin coated plate, total 2 wells, total 10 million mononuclear cells (prior to CD34 magnetic bead sorting) using CFU Hill Colony forming unit (Stem Cell Technologies- Cat#05900) media for Colony Forming unit (CFU) Assay. 2 days post plating, harvest non-adherent cells from each well, counted and will be replated at 1.0×10^6 cells/well in 12-well fibronectin coated plate. It is important that cell number of 1.0×10^6 is maintained in each well. CFU needs to be counted on Day 7 post plating (from initial plating).

From CD 34+ cell population (Post Sorting):

A. Migration Assay using SDF1 Alpha concentrations of 0, 10, 100ng/ml using 100,000 cells in 300ul serum free cell suspension media per insert. If sufficient cells are available we will note migration in response to VEGF-A (0, 20, 50 ng/mL).

SDF1 Assay alone will need $100,000 \times 9 = 0.9$ million cells. Use triplicates.

We will use 24 well plate using 3 micron pore migration membrane inserts from BD or Corning (354575).

Genes to be assessed on CD34 positive, CD34 negative cells:

Endothelial lineage cell surface markers: CD34, VEGFR2 (KDR), CD31, CD144

For Anti-oxidant gene expression: Superoxide dismutase (SOD) 1, 2 and 3, catalase, glutathione- peroxidase.

Apoptosis pathway: p53, p21, Bcl2, caspase-3

Endothelial Function Assay Gene: eNOS

Genes associated with progenitor cell chemotaxis: VEGF-A, SDF1 alpha, CXCR4

Secondary Measures:

- Highly selective C-reactive protein (hs-CRP), IL-6, IL-10, TNF-alpha, and fasting lipid profile including ApoA1 and ApoB (3, 6)
- Serum SOD activity and SDF1 alpha (ELISA), VEGF-A (ELISA) and GLP-1 (ELISA) levels will also be assessed (14, 20, 24, 39).

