- Assessment of insulin sensitivity using the HOMA-IR (32), calculated from individual serum measures (fasting glucose (mg/dl)* insulin (μU/mL)/405) [37].
- Adiposity will be measured using the Tanita Body Composition Analyzer scale, measured as percentage body fat, BMI, waist-hip measurements (5, 55)
- Fasting lipid profile will be checked as a marker of insulin resistance and lipotoxicity at weeks 0, 6 and 12.
- We also intend to acquire Pulse wave analysis and Vascular Flow using SphygmoCor CP system from ATCOR to measure central arterial pressure and arterial stiffness (38-42). The secondary measures are indirect measures of endothelial inflammation in early type 2 diabetes patients. (30, 31, 55, 56, 57).
- Obtain indirect calorimetric measurements of basal metabolic rate using machine obtained from Korrs Medical. This is a non invasive procedure. We plan to measure the oxygen that the body consumes. It will help us calculate a patient's Resting Energy Expenditure (REE), commonly referred to as a Resting Metabolic Rate (RMR). As our protocol is directed to overweight and obese individuals using incretin therapy, it will be beneficial to note if the treatment modifies RMR. Description: The machine ReeVue by KORR directly measures the concentration of oxygen breathed out by each patient. The patient breathes through a simple mouthpiece as all the exhaled air is collected and analyzed. Because there is a direct correlation between oxygen consumed and calories burned (4.813 calories for every milliliter of oxygen consumed), an accurate measurement of oxygen consumption is an effective measurement of calorie consumption. The machine uses a one-way valve in the disposable (MetaBreather) mouthpiece. This draws in fresh room air with each inspiratory breath and eliminates concerns about cross contamination. The disposable mouthpiece is thrown away. It is unnecessary to clean the equipment or the tubing between each patient. This

equipment is FDA approved and has been used in physician offices as an oxygen uptake test with associated CPT code #94690. (58)

- Urine pregnancy testing for women of child bearing potential
- Creatinine Clearance and proteinuria estimation via random spot urine.

We will obtain a total of 85 mL of peripheral blood per visit. Of these 85 mL, 60 mL will be used to obtain CD34+ cells from MNC population and 25 mL for biochemistry and serum ELISA assays.

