APPENDIX A: OPTIONAL URINE EXOSOME STUDY

A urine sample is already required as a part of [name] protocol. This urine will be used for urine pregnancy tests (if applicable), and labcorp tests for microalbumin/creatinine ratio. There will likely be excess urine.

Subjects will have the option to opt in or out of a research study in which the urine will undergo a urine exosome analysis.

Purpose of this Study: Exosomes are cell-derived vesicles that are present in many and perhaps all biological fluids, including blood, urine, and cultured medium of cell cultures. The reported diameter of **exosomes** is between 30 and 100 nm, which is larger than LDL, but much smaller than for example, red blood cells. Exosomes are either released from the cell when multivesicular bodies fuse with the plasma membrane or they are released directly from the plasma membrane.^[3] Evidence is accumulating that exosomes have specialized functions and play a key role in, for example, coagulation, intercellular signaling, and waste management.^[1] Consequently, there is a growing interest in the clinical applications of exosomes. Exosomes can potentially be used for prognosis, therapy, and biomarkers for health and disease. In this study we are particularly interested

in exosomes released from podocytes as a marker of podocyte function and podocyte inflammation. Podocytes are often considered a modified endothelium and one of its more commonly used parameter is microalbuminuria. In this study we are using urine exosomes as an added parameter of kidney function other than microalbuminuria and GFR calculation.

The procedure for this study is as follows:

From this sample, 10-20 mL of the fresh spot urine (or as much as possible) is placed into a urine cup containing 1 tab of cOmplete Ultra - protease inhibitor cocktail (Roche) for exosome analysis. The specimen can be refrigerated at 4°C for ~ 1 week or frozen at -80°C until assay, or will be processed for exosomes as follows;

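### SDF-1 alpha and GLP-1 are to be measured in serum with no enzyme inhibitor, handling conditions or ELISA form specified, so cleavage in the tube could differ by arm and mimic a drug effect on these secondary measures

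*Combined protocol and SAP*

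**What the plan says.** Section 2.2 fixes the matrix and the method: "Serum will be used to estimate levels of SDF1-Alpha, VEGF, and GLP1 levels by ELISA". The Secondary Measures list in section 4.5 repeats the assays: "Serum SOD activity and SDF1 alpha (ELISA), VEGF-A (ELISA) and GLP-1 (ELISA) levels will also be assessed".

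For handling, section 4.5 gives volumes only. Of 85 mL drawn per visit, "60 mL will be used to obtain CD34+ cells from MNC population and 25 mL for biochemistry and serum ELISA assays". An optional 95 mL draw at visits 2 and 3 leaves 20 mL for the same assays. For these blood samples the protocol does not state a tube additive, temperature, clotting time, time to separation, or whether the ELISA reads the intact or the total form.

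The Introduction supplies the biology. The hypothesis has linagliptin acting by "up-regulating chemotactic agent SDF1 alpha (DPP-4 degrades SDF-1) and its receptor CXCR4", and of DPP-4 inhibitors it says that "they increase bio-availability of endogenous GLP-1". Section 3.1 gives the expected direction: "Linagliptin along with other gliptins can increase SDF1 alpha levels".

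Samples are taken at week 0, when study drug is started, and on treatment at weeks 6 and 12. The Data Analysis text in section 5 makes the group-by-time interaction the contrast of interest.

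**The concern.** Both analytes depend on the enzyme that the study drug blocks. Serum has to stand while it clots. If DPP-4 keeps working in the tube, an assay that reads only the intact form records what is left after that delay, not what was in the patient.

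At week 0 neither arm's samples contain drug. At weeks 6 and 12 only the linagliptin samples do. Handling loss would then fall in the linagliptin arm after week 0 and stay the same in the placebo arm, which is the pattern that the interaction term detects. The artefact has the same sign as the hypothesised rise in SDF-1 alpha. Randomisation, masking and baseline adjustment do not remove it, because the drug in the sample causes it. What is at stake is whether a difference in serum SDF-1 alpha or GLP-1 may be read as evidence of mechanism.

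**Working it through.** The protocol gives no mean, SD or expected effect for SDF-1 alpha or GLP-1, so there is no stated figure to reproduce. What follows is an illustration with zero true effect.

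**Inputs from the protocol (section 5 and synopsis):** visits at weeks 0, 6 and 12; 18 completers per group; within-patient correlation 0.60; significance level 0.05, taken here as two-sided because sidedness is not stated.

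**Assumed inputs:** an intact-form assay; first-order loss in the tube with half-life h over a delay t; a share I of DPP-4 activity inhibited in linagliptin samples on treatment; analysis on the log scale with SD 0.3, 0.5 or 0.7. The protocol supplies none of these. Nor does it say that DPP-4 stays active in drawn blood or that linagliptin still inhibits it there.

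**Step 1, spurious ratio.** Placebo samples retain 2^(−t/h), and linagliptin samples on treatment retain 2^(−(1−I)t/h). With equal true levels, the measured ratio of linagliptin to placebo is 2^(I·t/h). At week 0 it is 1. Example with I = 0.8 and t/h = 1: placebo retains 0.500, linagliptin retains 2^(−0.2) = 0.871, and the ratio is 1.74.

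**Step 2, effect on the interaction.** A constant log shift at weeks 6 and 12 gives a slope difference of [6 × ln(ratio)]/72 = ln(ratio)/12, where 72 = 6² + 0² + 6² is the sum of squared deviations of the visit times.

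**Step 3, chance of a false significant result.** SE = sqrt(2·SD²·(1 − 0.60)/(18 × 72)). With SD 0.5 this is sqrt(0.2/1296) = 0.01242. At t/h = 0.5 the slope difference is 0.2773/12 = 0.0231, so z = 1.86 and the chance of p < 0.05 is Φ(1.86 − 1.96) + Φ(−1.86 − 1.96) = 46%.

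Results for I = 0.8:

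| Delay in half-lives | Spurious ratio | SD 0.3 | SD 0.5 | SD 0.7 |
|---|---|---|---|---|
| 0.1 | 1.06 | 10% | 7% | 6% |
| 0.25 | 1.15 | 34% | 15% | 10% |
| 0.5 | 1.32 | 87% | 46% | 26% |
| 1 | 1.74 | 100% | 96% | 76% |
| 2 | 3.03 | 100% | 100% | 100% |

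For I from 0.7 to 0.9 the ratio runs from 1.05 to 3.48. Complete inhibition is the upper limit: at two half-lives it would give 2² = 4.0. With a total-form assay, cleaved analyte is still counted and the ratio stays near 1 at any delay.

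**The case against.** A reader might infer that the tubes contain no inhibitor and that the serum results will be biased. The protocol does not support that. It is silent on tubes, temperature and spin times for these blood samples, and a laboratory manual not supplied here could add an inhibitor. Appendix A does specify a urine cup "containing 1 tab of cOmplete Ultra - protease inhibitor cocktail (Roche) for exosome analysis", but that is the procedure of an optional sub-study and does not show how blood is handled. The defensible statement is that no inhibitor is specified.

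The bias also needs an intact-form ELISA, and the form is not stated. A total-form assay would be nearly free of the artefact and could still address a rise in level, which is how section 3.1 words the expectation. It could not show protection from cleavage by DPP-4.

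The illustration runs from negligible to extreme. At 0.1 half-life the false-positive chance is 6% to 10%, little above the nominal 5%, and the protocol cannot say which row applies.

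Nor is the whole mechanism question exposed. CXCR4 by FACS, migration to fixed SDF-1 alpha concentrations, and SDF-1 alpha and CXCR4 gene expression (section 4.5) do not use serum. Neither analyte enters the sample size calculation.

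Finally, this is version 6.9 of June 2017, and the synopsis estimates first and last patients in September 2015 and September 2018. A change of matrix now could split the data.

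All of this stands as a limit on the point. It does not remove it. The protocol names serum, makes both analytes dependent on the inhibited enzyme, and sets no condition that would rule the artefact out.

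**Conclusion.** The point holds as a conditional one. If an intact-form ELISA is run on serum without an inhibitor, handling loss would differ by arm at weeks 6 and 12. It would then enter the group-by-time interaction for SDF-1 alpha and GLP-1 in the hypothesised direction.

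Its size cannot be derived from the documents. With 80% inhibition and delays of 0.1 to 2 half-lives, all assumed, equal true levels would read as a ratio of about 1.06 to 3.0. The effect is close to nil if the assay reads total analyte or the delay is negligible.

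A reader might go further and take the trial's main result to be compromised. That does not follow: these are secondary measures, and the CD34+ primary outcome is not affected. The point deserves more than a request for missing detail, because a better matrix is available at low cost and because the answer decides what these two assays may be used to conclude.

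**What to change.** - For SDF-1 alpha and GLP-1, collect chilled plasma in tubes containing a DPP-4 inhibitor, with protease inhibitor, handled identically in both arms at weeks 0, 6 and 12. State the time limit to separation and the storage conditions.
- State that the ELISA for these two analytes reads the intact form. Keep serum for the other analytes.
- Apply the new matrix only to patients who can have all three visits in it. Do not mix serum and plasma within a patient, and do not pool the two matrices in one model.
- For serum already collected without an inhibitor, state which form the ELISA reads, and do not interpret intact-form results as evidence of the SDF-1 alpha or GLP-1 mechanism.

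**Cost:** different tubes and a handling instruction, intended to fit within the 20 to 25 mL already set aside for biochemistry and ELISA. If the change comes mid-trial, the comparable set for these two secondary analytes will be smaller, and new plasma values cannot be compared directly with earlier serum values.

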3 INVESTIGATIONAL PLAN

3.1 Study Design and Duration

Study Schema, 40 Type 2 diabetic Subjects Aged 40-70 on stable dose of Insulin, Metformin, or both

+/- 3 day window for visits

*Assessed at week 0, 6 and 12: Biochemical and cellular markers of endothelial function and Pulse wave analysis and velocity (PWA and PWV), REE and Adiposity.

Week 16 - A telephone call to subjects will be made 30 days after last dose of study medication to determine if there have been any adverse events.

Available related studies and Expected Results: Studies measuring changes to EPCs in type 2 diabetes patients are very limited. To the best of our knowledge there are no studies examining the effect of Linagliptin in type 2 diabetes patients with CKD.

Use of CD34 positive cells as a cardiovascular risk surrogate has been reported in the past. Various studies (11, 34), have shown that various disease states, including those seen in diabetes, can deplete and damage EPC, thereby diminishing their regenerative potential. The inability to maintain or repair damaged endothelial tissue leads to cumulative vascular dysfunction and cardiovascular disease.

We hypothesize that monitoring **number, function and gene expression of endothelial progenitors will allow us to quantify cardiovascular disease risk at the onset and regenerative potential post intervention at a cellular level. It will also help us to identify and correlate the best endothelial function bio-chemical inflammatory marker as an early indicator of cardiovascular disease progression in early type 2 diabetes with CKD and identify patients that are responders.**

Linagliptin along with other gliptins can increase SDF1 alpha levels and possibly CXCR4 receptor expression which will help EPC mobilization and gene expression of hemopoietic CD34 positive stem cells.

Linagliptin 5 mg or placebo will be added to patients who have type 2 diabetes diagnosed ≤ 15 years with HbA1C of 6.5 to 10 % (both inclusive) while being on Insulin, metformin, or both.

Insulin will be titrated upwards if HbA1C is above 10% with minimal dose adjustments so as to keep the adjusted HbA1C below overtly uncontrolled levels (above 10%).

Our study population will include equal numbers of adult male and female Type 2 diabetes (T2DM) patients aged 40-70 years, enrolled in both arms of the study. Patients will be treated with 5 mg of Linagliptin or placebo for 12 weeks and with adequate lifestyle modification for 16 weeks (as per American Diabetes Association guidelines). This time interval has been previously shown to be adequate to observe changes to Endothelial Progenitor Cells (EPCs), (5, 6).

